### 5.1.1 Definition of Baseline

The first dosing visit in the OLE will be considered as baseline (OLE Day 1). The last available assessment made before or on OLE Day 1 will be considered the baseline assessment if occurring within 12 weeks before or on OLE Day 1 and prior to first dose for standard-of-care examinations or within 6 months for C-SSRS, cognitive scale results and MRI scans. For ADA data, baseline will be the baseline value of the parent studies to ensure that the baseline value is before any dose of the investigational product.

#### 5.2 PARTICIPANT DISPOSITION

The analysis of participant disposition will be based on all enrolled participants (see analysis sets in Section 4). The number of participants enrolled will be tabulated by country and site. Participant disposition (the number of participants enrolled, treated, and completing the study) will be tabulated. Premature study drug discontinuation and study discontinuation, as well as reasons for discontinuations, will be summarized.

Major protocol deviations, including major deviations with regard to the inclusion and exclusion criteria, will be summarized. Separate tables will be provided for COVID-19-related major protocol deviations and reasons for COVID-19-related major protocol deviations.

#### 5.3 PRIMARY ENDPOINTS ANALYSIS

### 5.3.1 Definition of Primary Endpoints

The primary objective for this study is to evaluate the safety and tolerability of long-term gantenerumab administered by SC injection on the basis of adverse events (AEs), physical examinations, vital signs, ECGs, laboratory tests, C-SSRS, ARIA-E and ARIA-H, ISRs, treatment discontinuations for AEs, and incidence of AEs of special interest.

The corresponding primary endpoints are:

- Nature, frequency, severity, timing, and outcomes of adverse events and serious adverse events
- Physical examinations (including neurologic systems), vital signs, ECG, laboratory tests, and Columbia-Suicide Severity Rating Scale (C-SSRS)
- Nature, frequency, severity, and timing of ARIA-E and ARIA-H

- Nature, frequency, severity, timing, and outcomes of ISRs
- Incidence of treatment discontinuations for adverse events
- Incidence of adverse events of special interest

The analytical approaches are described in pertinent subsection for each endpoint below.

### 5.3.2 Main Analytical Approach for Primary Endpoint(s)

All these safety analyses will be performed in the SE analysis set, except for analyses of ARIA-E or ARIA-H, CNS symptoms temporally associated with ARIA events or other MRI safety findings that will be based on the M-SE analysis set.

Participants will be analyzed according to the previous treatment they actually received in the parent studies and by participation / non-participation in the OLE part of the parent studies.

Descriptive statistics will be used to analyze all safety data collected in the study in the SE analysis set, unless otherwise specified.

Safety analyses will provide summaries of exposure to study treatment, adverse events, changes in laboratory test results (including shift tables), MRI findings, changes in vital signs and ECGs, and changes in C-SSRS scores as described in pertinent sections below.

### 5.3.3 Adverse Events

All verbatim AE terms will be coded using the Medical Dictionary for Regulatory Activities (MedDRA) version that is current at the time of the analysis (Version 25.0 or higher), and AE severity will be graded according to the scale defined in Table 3 in Section 5.3.3 of the study protocol (mild/moderate/severe). For each displayed participant group, the frequency of each AE preferred term will be defined as the number of participants experiencing at least one occurrence of the event. Each table will present the overall number and percentage of participants experiencing at least one AE and the total number of AEs reported. Percentages will be based on the number of participants in the SE analysis set. In summary tables, AEs will be sorted by body system (in decreasing order of overall incidence), then by preferred term (in decreasing order of overall incidence). The summary tables will be restricted to treatment-emergent AEs, i.e., AEs that occur or worsen on or after the day of first OLE dose, with onset no later than 14 weeks after last dose. Non-treatment-emergent AEs (AEs ongoing at OLE Day 1 with onset before the first OLE dose) and AEs occurring more than 14 weeks after the last dose will be listed.

The following safety information will be summarized:

- AEs, AEs by intensity, AEs related to study drug
- AEs with fatal outcome

- Serious AEs (SAEs), SAEs by intensity, SAEs related to study drug
- AEs leading to discontinuation of study treatment
- AEs leading to dose modifications (dose interruption, dose reduction, or delayed uptitration). Delayed up-titration at any given visit is defined as the simultaneous occurrence of the following two tickboxes in the eCRF Adverse Event form:
  - Action taken with open label gantenerumab due to SAE/AE: Dose Not Changed
  - If Dose not changed, was open label dose regimen modified from protocol schedule due to SAE/AE? Yes
- Injection site reaction (ISR) signs and symptoms
- Systemic injection reactions (AEs with "systemic reaction" selected)

Protocol-specified adverse events of special interest (AESI) will be listed.

The impact of the COVID-19 pandemic on the safety data will be assessed by reviewing the following:

- Confirmed or suspected COVID-19 AEs
- AEs associated with COVID-19
- Potential long COVID-19 symptoms

The following data handling rules will be applied for all AE summary tables:

- Events that are missing both onset and end dates will be considered to have started after the first dose of study drug and the duration will be set to missing.
- If the onset date is missing, and the end date is on or after the first dosing date or unresolved or missing, then the event will be considered to have started after the first dose of study drug.

The following data handling rules will also be applied for specific tables:

- An AE will be included in the summary table of AEs leading to study drug discontinuation if the "action taken with open label gantenerumab" drop-down menu on the AE eCRF is checked "drug withdrawn".
- In the summary table of AEs by intensity, if a participant has more than one
  occurrence of an event, the event with the most severe intensity will be counted. If
  the intensity of an AE is missing, then the AE will be included only in the total
  number of events column, and not in the count of participants with the event by
  intensity.
- In the summary table of AEs related to study drug, if a participant has more than
  one occurrence of an event, the related event will be counted if applicable. If the
  relationship of an AE is missing, then the AE will not be included in the count of
  participants with the event by relationship

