3.3.3.2 Rationale for the Subsequent 2-Year Duration

The extension of the study treatment duration from 2 to 4 years will allow the collection of more information on the long-term safety and tolerability of gantenerumab in AD and its efficacy in the context of long-term exposure. In addition, this will increase the overall number of participants exposed to gantenerumab and participant-years of exposure, thus increasing understanding of gantenerumab's long term safety and efficacy profiles.

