6.4 SAFETY ANALYSES

The safety analysis population will include all enrolled participants who received at least one dose of study drug in this protocol.

The following safety outcome measures will be summarized using descriptive statistics:

- Nature, frequency, severity, timing, and outcomes of adverse events and serious adverse events
- Physical examinations (including neurological systems), vital signs, ECG, laboratory tests, and C-SSRS
- Nature, frequency, severity, and timing of ARIA-E and ARIA-H
- Nature, frequency, severity, timing, and outcomes of injection-site reactions
- Incidence of treatment discontinuations for adverse events
- Incidence of adverse events of special interest

Statistical methods, endpoint definitions, and analyses of the safety endpoints will be described in a SAP.

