In this study, participants who were in the active double-blind arm in the parent study (GRADUATE I or GRADUATE II) will continue receiving open-label gantenerumab 510 mg subcutaneously (SC) every two weeks (Q2W), and those participants who were in the placebo double-blind arm will go through a full up titration scheme while retaining the blinding to the previous treatment allocation. Details of the dosing scheme are described in Section 4.3.2 of the study protocol. If there is a delay in a participant's transition between the OLE part of the parent study (GRADUATE I or GRADUATE II) and this study (for instance, due to delays in the approval of this study at a site) that goes beyond a reasonable time frame as determined by the Sponsor, the participant may be asked to start at the dose they were at previously when they completed the parent study and to perform a safety MRI before receiving the target dose. In this case, such decisions will be made after discussion with the Sponsor.

The dosing schedule and the schedule of activities will be different for participants, depending on whether they completed the OLE part of GRADUATE I or GRADUATE II study, which covers the up titration phase for the participants in the placebo arm, or if they completed only the double-blind part. Details are described in Appendix 1 of the study protocol.

Following baseline assessments (i.e., OLE Day 1 either in this protocol or in the parent protocol), each participant will be treated for 4 years. The study duration has been extended from 2 to 4 years to collect more information on the long-term safety and tolerability of gantenerumab in AD and its efficacy in the context of long-term exposure and to increase the overall number of participant-years of exposure, thus increasing understanding of gantenerumab's long-term safety and efficacy profiles. Unless participants are eligible and choose to enroll in an alternative gantenerumab OLE study that becomes available, the final dose of study drug will be administered at OLE Week 206. At the end of the treatment period, all participants will undergo an OLE Week 208 visit. Participants will be asked to come back for a follow-up visit at OLE

Week 220 unless they are transitioning to an alternative gantenerumab OLE study that becomes available.

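### Timing is a named part of the AE, SAE and ISR primary endpoints, but the SAP's AE tables have no time axis, so AEs and SAEs in the added years 3–4 cannot be separated from those in years 1–2

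*SAP*

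**What the plan says.** SAP 5.3.1 lists among the primary endpoints "Nature, frequency, severity, timing, and outcomes of adverse events and serious adverse events" and, separately, "Nature, frequency, severity, timing, and outcomes of ISRs". It adds that the analytical approach to each is set out in the subsections that follow. Protocol 6.4 introduces the same list with "The following safety outcome measures will be summarized using descriptive statistics" and refers to the SAP for methods.

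The relevant subsection is SAP 5.3.3. It sets one treatment-emergent window: "The summary tables will be restricted to treatment-emergent AEs, i.e., AEs that occur or worsen on or after the day of first OLE dose". At the other end, an event counts if it began within 14 weeks of the final dose. Each table gives the number and percentage of participants with at least one event, plus the total number of events. There are breakdowns by intensity, relatedness, seriousness, fatal outcome, discontinuation and dose modification, and a summary of ISR signs and symptoms. The denominator rule is "Percentages will be based on the number of participants in the SE analysis set". Columns are by previous treatment and by participation in the parent OLE (SAP 5.1 and 5.3.2). SAP 5.6.1 reports exposure separately, as overall duration, administrations and cumulative dose.

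On the extension, Protocol 3.3.3.2 says it "will allow the collection of more information on the long-term safety and tolerability of gantenerumab in AD", and SAP 1.2 says "The study duration has been extended from 2 to 4 years to collect more information on the long-term safety and tolerability of gantenerumab". Both sections also cite efficacy under long exposure and more participant-years. SAP Appendix 1, which records changes from the protocol's analyses, does not mention AE timing.

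**The concern.** A named attribute of two primary endpoints has no prespecified analysis. Nowhere does the SAP give an onset interval, a time to first onset, a person-year rate or an at-risk denominator for AEs, SAEs or ISRs.

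A cumulative percentage over everyone who started answers how many participants ever had an event while followed. It does not answer whether events become more or less common with longer treatment, which is a natural question for a study extended from 2 to 4 years partly for long-term safety. Because the denominator never shrinks, the late contribution looks small when many participants have left, whatever the rate among those remaining. In the previously-placebo columns the same figure also pools uptitration with later target dosing.

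**Working it through.** **1. Length of the window, checked against the plan's own figures.** The last dose is at OLE Week 206. Two-weekly visits from Week 36 to Week 206 number (206 − 36)/2 + 1 = 86, which reproduces the stated 86 doses after uptitration. The AE window for a completer ends at 206 + 14 = 220 weeks = 1,540 days = 1,540/365.25 = 4.22 years. That matches the Week 220 follow-up visit and the stated length of about 4 years and 3 months. The part after Week 104 is 220 − 104 = 116 weeks, and 116/220 = 53%.

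**2. Which safety data have a time axis.**

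| Data | SAP section | Time axis planned |
|---|---|---|
| Laboratory, vital signs, ECG | 5.3.5–5.3.7 | Yes, by visit |
| ARIA-E, ARIA-H | 5.3.4 | Yes, though timing is worded as optional; recurrence of ARIA-E also |
| Withdrawals, with reasons | 5.7.1 | Yes, by windowed visit |
| AEs, SAEs, ISRs | 5.3.3 | No |

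The interim analyses (SAP 5.8.1) reuse the 5.3.3 tables at a calendar cutoff, which does not sort events by time on treatment.

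**3. What the planned percentage can and cannot distinguish.** The documents give no AE or loss rates, so all rates here are assumptions. Let the first-event hazard be h1 in years 0–2 and h2 from year 2 to 4.22, and let a fraction d be lost per year, so the loss hazard is c = −ln(1 − d).

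- Early cases, as a share of all starters: A = h1/(h1 + c) × [1 − exp(−2(h1 + c))]
- Still observed and event-free at year 2: S = exp(−2(h1 + c))
- Late cases, as a share of all starters: B = S × h2/(h2 + c) × [1 − exp(−2.22(h2 + c))]
- Planned crude percentage: A + B

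Reference case, d = 10% and h1 = h2 = 0.10: c = 0.1054 and h + c = 0.2054. A = 0.487 × 0.337 = 16.4%. S = 66.3%. B = 0.663 × 0.487 × 0.366 = 11.8%. The crude value is 28.2%.

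Holding 28.2% fixed and solving for h1 at other ratios h2/h1:

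| h2/h1 | h1, h2 per 100 PY | A | S | B | Crude | B/S |
|---|---|---|---|---|---|---|
| 0.5 | 13.0, 6.5 | 20.7% | 62.5% | 7.5% | 28.2% | 12.0% |
| 1 | 10.0, 10.0 | 16.4% | 66.3% | 11.8% | 28.2% | 17.8% |
| 2 | 6.9, 13.7 | 11.6% | 70.6% | 16.6% | 28.2% | 23.5% |
| 3 | 5.2, 15.7 | 9.0% | 73.0% | 19.2% | 28.2% | 26.4% |

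The planned table shows only the crude column. An interval table would show A for the early period and, with an at-risk denominator, a quantity like B/S for the late one. The dilution is visible in the flat case: the late cases are 11.8% of starters but 17.8% of those still at risk.

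**4. Range.** With a constant hazard of 0.10 per year, the crude value is 31.2%, 28.2%, 23.0% and 18.7% at losses of 5%, 10%, 20% and 30% per year. It moves with loss although the event rate does not. At each of these losses, ratios from 0.5 to 3 can be made to give the same crude value.

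**The case against.** The strongest reply is that much of the safety picture does keep its timing. Laboratory data, vital signs and ECGs are by visit, ARIA timing is addressed, and withdrawals with reasons are by windowed visit, so a late rise in AE-driven discontinuation would show. A reader might infer that safety in years 3–4 is altogether invisible, or that a single percentage is all that is reported. The SAP does not support either: event totals and several breakdowns are given as well, although none is by time.

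A reader might also take long-term safety to be the only reason for the extension. It is one of several.

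Timing is not defined. For ISRs it could mean time from injection, since Protocol 5.3.5.1 limits injection reactions to within 24 hours of dosing. The ISR part is therefore weaker than the AE and SAE part.

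Output layouts are left to a separate Data Analysis Plan (SAP 1), which might contain an interval display. But intervals and denominators are methods, and the denominator rule in 5.3.3 is explicit, so this does not close the gap.

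The hazards above were solved to give equal percentages. They show that the table cannot discriminate between patterns. They do not show that any pattern is present.

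Finally, a careless interval table could mislead. SAP 5.1 acknowledges immortal time bias in parent-OLE participants, because those who stopped before consenting to this study are left out. Their early rates would look too low and later years too high by comparison. This stands, and it shapes the fix.

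**Conclusion.** The point holds for AEs and SAEs, and with less force for ISRs. SAP 5.3.3, followed as written, gives no information on when events occurred within a window of up to 220 weeks, 53% of which falls after Week 104, although timing is part of the primary endpoints and no change is declared. Under the assumed rates, late-to-early hazard ratios from 0.5 to 3 give the same crude 28.2%. That the table cannot separate them does not depend on the particular rates; the percentages do.

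A reader might go further and conclude that late safety information is lost. It is not: the AE form carries onset dates, the study is descriptive with no hypothesis to protect, and the tables could be produced later. What is missing is the prespecified analysis. This should be corrected in the SAP; it does not threaten the validity of the study.

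**What to change.** In SAP 5.3.3, add summaries of AEs, SAEs, related SAEs, fatal AEs and ISRs by yearly onset interval from OLE Day 1, specified as follows:

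- **Denominator:** participants still in the treatment-emergent window and under observation at the start of the interval, with events per 100 participant-years alongside.
- **Columns:** previous treatment and participation or non-participation in the parent OLE, both kept.
- **Parent-OLE participants:** either flag the time before rollover as subject to immortal time bias, or start their at-risk time at entry to WN42171.
- **Onset dates:** state how missing or partial dates are assigned, for example in a separate row for unknown onset. At present SAP 5.3.3 only places events without an onset date after the first dose (unless they ended before it), and SAP 5.1 rules out imputation.
- **After the last dose:** show the 14-week period separately from on-treatment time.
- **ISRs:** say whether timing means time on treatment, time from injection, or both.

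The cost is SAP wording, date rules and a set of additional tables on AE and dosing dates already collected; no new data are needed. Outputs become longer and later denominators smaller. Late-interval rates will reflect selective drop-out as well as any drug effect, without a concurrent untreated comparator, so the SAP should say that they are to be read descriptively.

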4.6 TREATMENT, PARTICIPANT, STUDY, AND SITE DISCONTINUATION

4.6.1 Study Treatment Discontinuation

Participants must permanently discontinue study treatment if they experience any of the following:

- Any medical condition that the investigator or Sponsor determines may jeopardize the participant's safety if he or she continues to receive study treatment
- Investigator or Sponsor determination that treatment discontinuation is in the best interest of the participant
- Pregnancy
- Evidence of an intracerebral macrohemorrhage
- Evidence of disseminated leptomeningeal hemosiderosis

The primary reason for study treatment discontinuation should be documented on the appropriate eCRF. Participants who discontinue study treatment prematurely will not be replaced.

All participants who withdraw from treatment will be asked to return 2 weeks after their final dose in order to complete the early termination visit assessments.

In addition, participants who withdraw from treatment will be asked to return for collection of safety data (except MRI) and limited efficacy data (i.e., secondary endpoints) at visits that have efficacy assessments (e.g., OLE Week 52, OLE Week 76, OLE Week 104, *OLE Week 130, OLE Week 156, OLE Week 182, OLE Week 208, and OLE Week 220*) according to the schedule of activities.

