5.3.5.9 Deaths

All deaths that occur during the protocol-specified adverse event reporting period (see Section 5.3.1), regardless of relationship to study drug, must be recorded on the Adverse Event eCRF and immediately reported to the Sponsor (see Section 5.4.2). This includes death attributed to progression of AD.

Death should be considered an outcome and not a distinct event. The event or condition that caused or contributed to the fatal outcome should be recorded as the single medical concept on the Adverse Event eCRF. Generally, only one such event should be reported. If the cause of death is unknown and cannot be ascertained at the time of reporting, **"unexplained death"** should be recorded on the Adverse Event eCRF. If the cause of death later becomes available (e.g., after autopsy), "unexplained death" should be replaced by the established cause of death. The term **"sudden death"** should not be used unless combined with the presumed cause of death (e.g., "sudden cardiac death").

If the death is attributed solely to progression of AD, "Alzheimer's disease progression" should be recorded on the Adverse Event eCRF.

Deaths that occur after the adverse event reporting period should be reported as described in Section 5.6.

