### 2. STATISTICAL HYPOTHESES

All analyses provided in this document are descriptive, thus no statistical hypothesis will be tested in these analyses.

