### 3. SAMPLE SIZE DETERMINATION

The sample size will be determined by the number of participants who complete the parent studies (GRADUATE I and GRADUATE II) and enroll in this study. The sample size is expected to be no more than approximately 2032 participants.

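### The AE, SAE and fatal-AE tables stop at onset 14 weeks after last dose; later events are only listed, and the SAP specifies no whole-study count of deaths or SAEs

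*SAP*

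**What the plan says.** SAP 5.3.3 limits its AE summary tables to treatment-emergent events, meaning events that start or worsen on or after the first OLE dose, "with onset no later than 14 weeks after last dose". The outputs under that rule include SAEs and "AEs with fatal outcome". Percentages use the whole safety-evaluable (SE) set as denominator. For later onsets the rule is "AEs occurring more than 14 weeks after the last dose will be listed". SAP 5.6.1 summarises treatment duration, number of administrations and cumulative dose. It plans no person-years of follow-up.

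The protocol's collection rules are not tied to the last dose:

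- Protocol 4.6.1: "participants who withdraw from treatment will be asked to return for collection of safety data (except MRI) and limited efficacy data", at the efficacy visits through OLE Week 220. Section 4.5.13 repeats this and has autopsy reports requested for deaths before the Week 220 visit.
- Protocol 5.3.1 runs AE reporting to the participant's final visit in the study.
- Protocol 5.3.5.9 covers "All deaths that occur during the protocol-specified adverse event reporting period", whatever their relation to drug and including death from progression of Alzheimer's disease. Each death is recorded through the event that caused it.
- Protocol 6.4 lists among the measures to be summarised: "Nature, frequency, severity, timing, and outcomes of adverse events and serious adverse events". It states no post-dose limit and leaves methods and endpoint definitions to the SAP.

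**The concern.** How long a participant stays on drug is itself a post-baseline outcome. Under the SAP rule, the length of time over which a death or SAE can reach a summary table depends on it, while the denominator does not. A participant who stops at Week 52 and has a fatal event starting at Week 80 stays in the denominator of the fatal-AE percentage but not in its numerator.

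The percentage is then lower than the proportion of the cohort known to have died, and the gap is larger in a column where more people stop. A reader of a study extended to four years for long-term safety will want to know how many participants died and how many had an SAE, on or off drug. On the SAP as written, that reader would have to add up a listing, with no person-time to set it against.

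**Working it through.** **Inputs.** Planned final dose Week 206 and last visit Week 220 (Protocol 3.1.1, SAP 1.2); post-dose window 14 weeks (SAP 5.3.3); return visits for those off drug at Weeks 52, 76, 104, 130, 156, 182, 208 and 220 (Protocol 4.6.1).

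**1. The plan's own figure.** 220 − 206 = 14 weeks, which equals the SAP window. The SAP does not say this is where the figure comes from, but the match means that nothing planned for a completer falls outside the tables.

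**2. Early stoppers.** For last dose at week w with follow-up to Week 220: off-drug time = 220 − w; in the tables = 14; listed only = 206 − w.

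| Last dose (week) | Off-drug weeks | In tables | Listed only | Share listed only |
|---|---|---|---|---|
| 52 | 168 | 14 | 154 | 92% |
| 104 | 116 | 14 | 102 | 88% |
| 156 | 64 | 14 | 50 | 78% |
| 182 | 38 | 14 | 24 | 63% |
| 206 | 14 | 14 | 0 | 0% |

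After a last dose at Week 52, 104 or 156, the next efficacy visit (Week 76, 130 or 182) is 24, 26 or 26 weeks away, so all of those return visits lie beyond the window. The early termination visit, 2 weeks after last dose, lies inside it. The cut is on onset, so an event that began within 14 weeks and is reported at a later visit still counts.

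**3. Possible number of deaths affected (illustration only).** The documents give no rates. Assume that 5–15% of participants stop drug per year, 1–3% die per year (the same on and off drug), and a fraction r = 25–100% of stoppers stay in follow-up to Week 220. Take N = 2032, which is a ceiling: "The sample size is expected to be no more than approximately 2032 participants". Treat date of death as date of onset. With weekly hazards a = −ln(1 − annual stopping)/52 and m = −ln(1 − annual mortality)/52, deaths outside the window are

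N · r · e^(−14m) · { a/(a+m) · [1 − e^(−206(a+m))] − e^(−206m) · [1 − e^(−206a)] }.

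For 10% stopping, 3% mortality and r = 1: a = 0.002026, m = 0.000586, and 2032 × 0.9918 × (0.3228 − 0.3025) ≈ 41 deaths outside the window against about 205 inside. That is 41/246 ≈ 17%. Across the assumed ranges the result runs from about 2 to 59 deaths, or 2% to 24% of deaths during follow-up.

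**4. Effect on a comparison between columns.** Keep 3% annual mortality and r = 1, and compare 5% with 15% stopping per year:

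- 5% stopping: 224.3 deaths inside + 21.4 outside = 245.7. Tabulated: 224.3/2032 = 11.0%.
- 15% stopping: 186.6 inside + 59.1 outside = 245.7. Tabulated: 186.6/2032 = 9.2%.

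True mortality is 245.7/2032 = 12.1% in both. The column with more stopping looks safer only because fewer of its deaths fall inside the window.

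**The case against.** Several arguments on the other side hold, and they limit the point.

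- A treatment-emergent window is standard and fits an objective about the drug as administered. It gives everyone the same post-dose risk period. This stands, and the main tables should not change.
- A reader might infer that off-drug safety follow-up enters no count at all. The documents do not support that. The first 14 off-drug weeks are in every AE table. The laboratory, vital-sign, ECG and C-SSRS summaries (SAP 5.3.5 to 5.3.8) carry no such limit. Drug and study discontinuations with reasons are tabulated for all enrolled participants (SAP 5.2).
- A reader might infer that no all-cause death figure is produced. Within its onset window the fatal-AE table is all-cause, because any death is recorded through its causing event. A death after 14 weeks from an event that began earlier is included. What is missing is an all-cause count over the whole study.
- A reader might infer that the SAP contradicts Protocol 6.4, or that Appendix 1 had to declare the window. Section 6.4 delegates methods to the SAP, so at most this is a matter of transparency.
- The weeks in the table are ceilings. The protocol only asks stoppers to return, and SAP 1.2 offers completing the safety follow-up as an alternative, so later data may be sparse.
- Nothing formal is compared: "All analyses provided in this document are descriptive, thus no statistical hypothesis will be tested in these analyses". True, but the columns will be printed side by side and read that way.
- Death may appear among the reasons for study discontinuation, and output layouts sit in separate Data Analysis Plan modules. SAP 5.2 does not name death as a category, and disposition would not count later SAEs. The safe statement is that this SAP specifies no such count.

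**Conclusion.** The point holds as a gap in reporting. No data are lost, since later events are still listed. What is missing is a whole-study count, with a denominator in time, of two outcomes the protocol deliberately keeps collecting.

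The share of off-drug time left to a listing is fixed by the schedule, given that the participant stays to Week 220. The number of deaths and SAEs affected cannot be derived from the documents. The range of 2% to 24% of deaths rests entirely on assumed stopping, mortality and retention, and its low end is negligible. That frailer participants stop first is plausible but not shown. The illustration does not need it, because unequal stopping alone distorts the columns. This is a cheap improvement worth making and does not invalidate the planned safety analysis.

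**What to change.** Keep the treatment-emergent tables as the main ones. Add to SAP 5.3.3 one supportive table in the SE set, by the planned columns (previous treatment, and participation or not in the parent OLE part), covering first OLE dose to last contact:

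- all deaths from any cause, by date of death;
- all SAEs, by date of onset;
- each split into up to 14 weeks after last dose and later, with person-years for each segment.

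A line in Appendix 1 naming the 14-week restriction would help the reader but is optional.

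The cost is one table from data already collected. It mixes on-drug and off-drug time, so its title must say that it is not an on-drug rate. Two footnotes are needed. A late death from an early-onset event will sit in the later segment here but in the main fatal-AE table there. For participants who came through the parent OLE part, the person-years before rollover carry the immortal time that SAP 5.1 already acknowledges.
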